### **7.3 Dexamethasone**

Commercial dexamethasone will be used for this trial. Dexamethasone is available in 4 mg tablets. Dexamethasone should be stored at room temperature away from direct sunlight and protected from excessive heat and cold.

#### **7.3.1 Dosing Information**

Patients will be instructed to take Dexamethasone 40 mg (10 tablets) orally once weekly with meals (ideally with breakfast to minimize insomnia). Patients 75 years or older and patients previously intolerant to 40 mg dosage will be allowed to receive 20 mg (5 tablets) once a week.

## 8 TOXICITIES, RISKS, AND AE-RELATED DOSE MODIFICATIONS

### 8.1 Selinexor

#### 8.1.1 Selinexor Toxicity Overview

Selinexor is currently in clinical development and has not been FDA-approved for use. Human experience with selinexor is currently limited and the entire safety profile is not known at this time. Measures will be taken to ensure the safety of the patients participating in this trial, including the use of stringent inclusion and exclusion criteria and close monitoring. Toxicity grading will be performed in accordance with NCI CTCAE 4.03. If more than one different type of toxicity occurs concurrently, the most severe grade will determine the modification.

If toxicities are encountered, adjustments will be made to the study treatment as detailed in the sections below. All AEs grade >1 and SAEs will be recorded during the trial and for up to 30 days after the last dose of study treatment or until the initiation of another anti-cancer therapy, whichever occurs first.

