### 8.1.4 Dose Adjustment Guidelines for Selinexor-Related Toxicities

**Table 2 Selinexor-related toxicity management guidelines**

Toxicity and Intensity	Dose Modification
Fatigue (common)	
Grade 1	Ensure adequate caloric intake and assess volume status. Rule out other causes of fatigue such as pain, anemia, or adrenal insufficiency.
Grade 2	Ensure adequate caloric and fluid intake and assess volume status. If fatigue does not improve with conservative measures, consider dose reduction selinexor by one level.
Grade 3	Ensure adequate caloric and fluid intake and assess volume status. Interrupt selinexor dosing until resolved to Grade $\leq 2$ , reduce dose of selinexor by 1 level
Anorexia (common)	
Grade 1	Assess dietary options (e.g., try a variety of other foods). Add high-calorie supplements (e.g., Ensure®).
Grade 2	Add high-calorie supplements (e.g., Ensure®). Consider olanzapine 2.5 - 5mg po qhs (especially if nausea or sleep disturbance present). Consider megesterol acetate 400-800mg daily. Consider dronabinol (Marinol®). Skip intermittent doses of selinexor while supportive medications are instituted. If Grade 2 anorexia does not resolve after institution of supportive medications, reduce selinexor dose by 1 level.
Grade $\geq 3$	Interrupt dosing with selinexor. Add high calorie supplements. Use supportive medications alone or in combinations. Restart selinexor at 1 dose level reduction once anorexia resolves to Grade $\leq 2$ . If Grade 2 anorexia persists with supportive medications, reduce dose of selinexor another dose level.
Nausea/Emesis (common)	
Grade 1	5-HT3 antagonists, D2 antagonists, olanzapine 5mg qhs or 2.5mg bid, NK1 antagonists, or dronabinol (Marinol) or combinations can prevent nausea in the majority of patients.
Grade 2	Implement one or more combinations of anti-nausea medications. If nausea does not

	resolve to Grade $\leq 1$ , reduce dose of selinexor by one dose level.
Grade 3	Implement one or more combinations of anti-nausea medications and interrupt dosing of selinexor. Selinexor may be restarted with one dose level reduction when nausea is Grade $\leq 2$ and adequate caloric and fluid intake have been achieved.
Hematologic	
Neutropenia (rare)	

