Grade 1 (ANC < LLN - 1500/mm  ) Grade 2 (ANC < 1500 - 1000/mm  ) Grade 3 (ANC < 1000 - 500/mm  )	Maintain dose level The use of growth factors during selinexor treatment is permitted during the phase II and after cycle 1 is completed in the phase I.
Grade 4 (ANC < 500/mm  )	Hold study treatment until ANC returns to >800/mm  . Dose reduce LD (if appropriate) and consider growth factor support.
Febrile neutropenia, or fever of unknown origin without clinically or microbiologically documented infection (ANC < 1.0 x 10  /L, fever $\geq$ 38.5°C)	Hold study treatment until patient has stabilized. Dose reduce LD (if appropriate) and consider a dose reduction in selinexor
Thrombocytopenia (Platelets) (uncommon)	
Grade 1 (PLT < LLN - 75,000/mm  ) Grade 2 (PLT < 75,000 - 50,000/mm  )	Maintain dose level.
Grade 3 (PLT < 50,000 -25,000/mm  ) without bleeding	Maintain dose level
Grade 4 (PLT < 25,000/mm  ) without bleeding	Delay study treatment until resolved to $\leq$ grade 3. Dose reduce LD (if appropriate) and / or selinexor Platelet transfusions may be given to support platelet levels in patients with clear clinical benefit from selinexor.
Grade $\geq 3$ with bleeding	Delay study treatment until resolved to $\leq$ grade 2, reduce dose by 1 level when resolved.
Hyponatremia (common)	
Grade 1 (Lower Limit of Normal to 130nM)	Maintain dose level, assure adequate fluid, electrolyte and caloric intake, adjust other medications, consider salt supplementation, rule out other causes.
Grade 3 (120-130nM)	Discontinue selinexor until resolved to grade $\leq 1$ then consider reducing dose by 1 level

	especially if another cause is not identified. Check renal function, serum and urinary electrolytes, and rule out other causes.
Diarrhea (uncommon)	
Grade 1 (despite maximal anti-diarrheal medication)	At the first sign of abdominal cramping, loose stools, or onset of diarrhea, it is recommended that the patient be treated according to institutional standard of care. Maintain dose level of selinexor.
Grade 2 (despite maximal anti-diarrheal medication)	Hold therapy. If diarrhea returns as $\geq$ Grade 2, then reduce selinexor dose by one dose level until resolved to $\leq$ grade 1
Grade 3/4 (despite maximal anti-diarrheal medication)	Delay selinexor until resolved to $\leq$ grade 2, then follow guidelines above.
Other adverse events	

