Grade 1 or 2	Maintain dose level and initiate standard supportive care.
Grade 3	Delay dose until resolved to $\leq$ Grade 1, then reduce by 1 dose level
Grade 4	Discontinue selinexor and rule out other causes. If other causes of Grade 4 adverse event are uncovered, selinexor may be re-initiated at 1 dose level reduction.

All dose modifications should be based on the worst preceding toxicity.
 
Isolated values of <math>\geq</math> grade 3 alkaline phosphatase values will NOT require dose interruption. Determination of liver vs. bone etiology should be made, and evaluation of GGT, 5'NT, or other liver enzymes should be performed.
 
<math>\geq</math> Grade 3 anemia judged to be a hemolytic process secondary to study drug will require interruption of study treatment until resolved to <math>\leq</math>Grade 1. Selinexor may then be re-instituted at 2 levels below original dose.
 
<math>\geq</math> Grade 3 lymphopenia considered clinically significant will require dose interruption until resolved to <math>\leq</math> grade 2, then reduce by 1 dose level.
 
Patients are allowed dose reductions to a minimum dose of 5mg/m^2. If a patient requires a dose interruption of > 28 days, then the patient must be discontinued from the study. Patients who discontinue the study for a study related adverse event or abnormal laboratory value must be followed at least once a week for 28 days and subsequently at 28 day intervals until resolution or stabilization of the event, whichever comes first.
 
a. Common Terminology Criteria for Adverse Events (CTCAE Version 4.03 ) otherwise specified values.
	

- For all  $\geq$  Grade 3 hematological or non-hematological AEs that are NOT selinexor related: After consultation with the principal investigator and at the discretion of the treating physician, selinexor dosing may be maintained provided that the patient can continue to take the agent by mouth, or via other enteral route.

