Grade 3 (blistering, ulceration, or swelling interfering with walking or normal daily activities; cannot wear regular clothing) Grade 4 (diffuse or local process causing infectious complications, or a bed ridden state or hospitalization)	Delay dosing up to 2 weeks or until resolved to Grade 0-1. Decrease Liposomal doxorubicin by 1 dose level and return to original dose interval. If after 2 weeks there is no resolution, Liposomal doxorubicin should be discontinued.
Neutropenia	
Grade 1, 2, 3	Maintain dose level. Growth factor support is permitted during the phase II portion and the

	phase I after cycle 1.
Grade 4	Hold study treatment until ANC returns to >800/mm  . Reduce Liposomal doxorubicin by 1 dose level. Recommend growth factor support if not already implemented
Febrile Neutropenia	Hold study treatment until patient has stabilized. Dose reduce LD by 1 dose level and recommended growth factor support
Thrombocytopenia	
Grade 1,2,3 without bleeding	Maintain dose level
Grade 4 or grade 3 with clinical bleeding	Delay study treatment until resolved to thrombocytopenia is resolved to grade 3 or less and bleeding stopped. Reduce LD by 1 dose level. Platelet transfusion are allowed per routine clinical care
Serum Bilirubin (when not related to Gilbert's Syndrome)	
1.2 – 3.0 mg/dL	Reduce LD by 25%
> 3 mg/dL	Reduce LD by 50%
Cardiac Toxicities	
Arrhythmia ≥ grade 2	Hold Liposomal doxorubicin until resolved to ≤ grade 1. Decrease Liposomal doxorubicin by 1 dose level
Arrhythmia ≥ grade 3	Discontinue Liposomal doxorubicin. Patients may continue on selinexor if there is a clinical benefit in the opinion of the investigator
Congestive heart failure ≥ grade 2	Discontinue Liposomal doxorubicin. Patients may continue on selinexor if there is a clinical benefit in the opinion of the investigator
Asymptomatic decrease in ejection fraction by 20% or more	Discontinue Liposomal doxorubicin
Other non-hematologic Adverse Events	
Grade 1, 2	Maintain dose level and initiate standard supportive care
Grade 3	Delay dose until resolved to grade 1 or less, then reduce by 1 dose level
Grade 4	Discontinue Liposomal doxorubicin

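### Section 8.1.1 ranks concurrent toxicities by grade alone, but in Table 2 two Grade 3 cytopenias leave the selinexor dose unchanged while two Grade 2 events interrupt it

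*Combined protocol and SAP*

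**What the plan says.** Section 8.1.1, under Selinexor, settles concurrent toxicities in one sentence: "If more than one different type of toxicity occurs concurrently, the most severe grade will determine the modification". Its next paragraph refers adjustments of the study treatment to the sections that follow. A note at the foot of Table 2 adds a second rule: "All dose modifications should be based on the worst preceding toxicity".

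Table 2 (selinexor) then gives actions row by row:

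- Neutropenia of Grades 1 to 3 shares one instruction, which begins "Maintain dose level The use of growth factors during selinexor treatment is permitted during the phase II".
- The thrombocytopenia row labelled "Grade 3 (PLT < 50,000 -25,000/mm 3 ) without bleeding" also leaves the dose as it is.
- Grade 2 diarrhea begins "Hold therapy. If diarrhea returns as" and continues with a reduction on recurrence.
- Grade 2 anorexia includes "Skip intermittent doses of selinexor while supportive medications are instituted", with a reduction if the event does not resolve.

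Table 3 (liposomal doxorubicin, LD) has the same pattern. For neutropenia of Grades 1 to 3 it says "Maintain dose level. Growth factor support is permitted during the phase II portion", and thrombocytopenia of Grades 1 to 3 without bleeding is treated alike. Grade 2 stomatitis and Grade 2 hand-foot syndrome (HFS) delay LD, Grade 2 arrhythmia holds it, and the row "Congestive heart failure ≥ grade 2" discontinues it.

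Two other places bear on the question. Section 8.1.3 allows one or two selinexor doses to be held for Grade 2 or lower toxicities. Section 3.1.2 sets recovery conditions for starting a new induction cycle.

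**The concern.** Deciding by the highest grade is safe only if a higher grade always carries an action at least as strict as a lower grade of any other toxicity. These tables are not built that way. A patient with a drug-related Grade 3 cytopenia and a Grade 2 event that calls for interruption has two instructions: the row for the Grade 2 event stops the drug, and the concurrent-toxicity rule points to the cytopenia row, which does not.

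The first issue is safety, because a rule in the protocol, read as written, displaces an interruption that the protocol's own table calls for. The second is consistency. Section 3.1 names three centers, and dose intensity in phase II would depend on which text a site follows.

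**Working it through.** The plan gives no figure here to reproduce, so the check sets the rows side by side and counts contradictions. A pair counts as a direct conflict when the higher-grade row leaves the dose unchanged and a lower-grade row for a different toxicity holds, skips, delays or stops the drug unconditionally.

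**Step 1. Table 2, selinexor (Section 8.1.4).**

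| Higher grade, dose unchanged | Lower grade, dosing interrupted |
|---|---|
| Grade 3 neutropenia | Grade 2 diarrhea |
| Grade 3 thrombocytopenia without bleeding | Grade 2 anorexia |

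Every row on the left conflicts with every row on the right: 2 × 2 = 4. Four further pairs set the same cytopenias against Grade 2 fatigue and Grade 2 nausea. There a reduction is only considered or is conditional on non-response, so these pairs are not counted.

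**Step 2. Table 3, LD (Section 8.2.4), if the rule reaches it.** The same two cytopenias leave LD unchanged. Four Grade 2 rows are stricter: stomatitis, HFS, arrhythmia and congestive heart failure. That gives 2 × 4 = 8. Pairs with Grade 1 stomatitis or HFS are left out, because those rows delay LD only after an earlier Grade 3 or 4 event.

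**Step 3. How widespread the pattern is.** Direct conflicts total 4 + 8 = 12, all from two Grade 3 cytopenias. Those account for 2 of 12 Grade 3-or-higher entries in Table 2 and 2 of 10 in Table 3, so 4 of 22. The denominators shift slightly if combined rows such as Grade 3/4 are split. Within any one toxicity, no higher grade leaves the dose unchanged while a lower grade interrupts it. The problem appears only across toxicities, which is the case the sentence in Section 8.1.1 addresses.

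**Step 4. Grade 4 neutropenia with Grade 3 fatigue, anorexia or nausea.** The neutropenia row holds study treatment until the ANC exceeds 800/mm³ and names only an LD reduction. The three Grade 3 rows interrupt selinexor and provide for a one-level reduction. Both sides stop selinexor. Only whether the selinexor reduction applies is unclear. Above 800/mm³ the neutropenia is Grade 3 at most, so it no longer outranks the other event, and the rule does not cover ties.

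**Step 5. Does other text resolve the conflict?**

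- The Table 2 note does not say whether *worst* means highest grade or strictest action.
- Section 8.1.3 permits a hold for Grade 2 or lower events but does not require one, and it does not mention a concurrent higher-grade cytopenia.
- Section 3.1.2 governs the start of a cycle. Selinexor at dose level 2m is also given on Days 8 and 15, which it does not cover. Its phase II text sends the reader to Section 6.1 for non-hematologic recovery, and Section 6.1 (study assessments) has no recovery criteria. Its general condition accepts other drug-related events once they are at Grade 2 or below, which is the grade at issue.

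**The case against.** The best defense is that *maintain* means no reduction on account of the cytopenia, and does not forbid a hold for something else. A sensible clinician would probably read it so, and Section 8.1.3 gives separate permission to hold selinexor for low-grade events. This softens the practical risk but does not remove the contradiction. Section 8.1.1 says that the most severe grade determines the modification, and in these pairs the call to interrupt stands in the lower-grade row. A permission to hold is also weaker than a row that calls for one.

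For LD the defense is stronger. The sentence stands under Selinexor and is not repeated in Sections 8.2 or 8.3. LD is given only on Day 1, where the Section 3.1.2 conditions apply, and for phase I these point correctly to Section 8. So the eight Table 3 conflicts are conditional. They depend on reading the reference to study treatment and later sections as extending the rule to LD. If the rule does not extend, LD has no concurrent-toxicity rule and the four selinexor conflicts remain.

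A reader might also infer that a phase II patient admitted with platelets between 30,000 and 50,000/mm³ is under the override from the start of treatment. The documents do not support this. Table 2 covers selinexor-related toxicity, and Section 3.1.2 treats cytopenias from the underlying disease separately.

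**Conclusion.** The contradiction is real and narrow: four direct conflicts for selinexor and, on an inferred reading, eight more for LD. It rests on the literal wording of Section 8.1.1 and on the rows of Tables 2 and 3 as extracted. It should be corrected because it concerns interruptions for toxicity in a trial that treats patients at several sites.

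Three stronger conclusions are tempting and should not be drawn. A reader might infer that the tables are generally inverted, but only two Grade 3 cytopenias produce direct conflicts. A reader might infer that Grade 4 neutropenia cancels the selinexor interruption for a Grade 3 event, but both rows stop the drug. A reader might infer that the DLT count, and so the chosen dose, is unsound. Section 6.1.4 does count a missed dose due to toxicity as a DLT, so the ambiguity could have affected individual phase I classifications. But Section 1.5.2 reports that dose level 2m was already found to be the recommended phase II dose, and nothing shows that any case turned on this. The DLT point therefore bears only on interpreting phase I.

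How often the conflict would arise cannot be estimated. Sections 8.1.2 and 8.2.2 list the events involved as common, but without grades or joint frequencies.

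**What to change.** Reconcile the sentence in Section 8.1.1, the note under Table 2, the optional holds in Section 8.1.3, the cycle-start conditions in Section 3.1.2 and Tables 2 to 4. The protocol should state once, for each of the three drugs, how concurrent toxicities are handled when their rows call for different actions. The text should:

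- say whether the rule in Section 8.1.1 applies to LD and dexamethasone;
- define *worst* in the Table 2 note;
- cover equal grades and the rows with no grade (bilirubin, ejection fraction);
- cover mid-cycle selinexor doses;
- correct the phase II pointer to Section 6.1.

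The clinical content is for the investigators to decide. The cost is a few sentences in an amendment, with no added data, visits or patients. When phase I is reported, any cycle 1 dose held or given in the presence of two concurrent toxicities should be described, so that readers can see how the ambiguity was handled.

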#### 8.1.2 Risks Associated with Selinexor

As of June 2013, 96 human patients have been treated with selinexor. Across these trials, 9 patients of 97 (9.3%) have reported at least one SAE that is at least possibly related to study drug. Side effects observed in these patients include:

**Very common side effects (≥10%):**

- Nausea
- Vomiting
- Diarrhea
- Anorexia
- Hyponatremia
- Dehydration
- Blurred vision
- Thrombocytopenia
- Anemia
- Neutropenia
- Leucopenia
- Fatigue
- Weight Loss
- Dysgeusia
- Dizziness

**Common side effects (≥1-10%):**

- Constipation
- Dry mouth
- Creatinine Increased
- Worsening of pre-existing cataracts
- Febrile neutropenia
- Dyspnea
- Syncope
- Confusion
- Pneumonia

Sepsis

**Uncommon side effects (>0.1-1%):**

Cognitive disturbance

Altered balance

**Rare side effects (>0.1-1%):**

Acute cerebellar syndrome – symptoms can include a sudden loss of coordination, balance, or slurred speech

**Reproductive risks**

Patients should not become pregnant or father a baby while on this study because the drugs in this study can affect an unborn baby. Women should not breastfeed a baby while on this study. It is important patients understand the need to use birth control while on this study.

**8.1.3 Dose Modifications for Selinexor**

Based on observations from the ongoing Phase I studies in patients with advanced hematological and solid tumors, selinexor shows a reasonably wide therapeutic range, with activities from ~12mg/m^2 to 35mg/m^2. At the present time, we do not know how to predict which patient's tumors will respond to lower doses, nor can we predict tolerability. Therefore, in order to optimize specific anti-tumor activity and the patient's tolerability, therapy is initiated at 80mg weekly. In patients with tolerability issues on selinexor, we recommend reducing the selinexor dose. In addition, if patient is experiencing one or more Grade ≤2 toxicities such as fatigue or anorexia, then 1-2 doses of selinexor can be held, and dosing resumed at current dose.

Toxicity will be graded according to NCI CTCAE, version 4.03; the therapy modifications described below are applied according to this severity grading. If drug-related toxicity requires a treatment delay of more than 4 weeks, then the patient is taken off protocol treatment. Each dose modification or treatment delay has to be documented in the CRF, including the respective reason.

Phase I data in patients with both solid and hematologic malignancies indicate that selinexor is associated with minimal laboratory abnormalities. Therefore, provided that it is clinically indicated, patients should be treated aggressively with supportive care to reduce

**Table 1: Prespecified dose modifications for adverse events related to study drug**

toxicities and permit selinexor dosing to be maintained at the same or reduced doses/frequency as indicated below.

Dose levels 1	60 mg D1,8, 15
Dose levels -1	40 mg D1,8,15
Dose levels -2	20 mg-D1,8,15

Dose levels 2	80 mg D1,8, 15
Dose levels 3	80 mg D1,3,8, 10

Intra-patient dose escalation for selinexor will be allowed at the discretion of the treating physician and principal investigator provided the above dose level was found to be tolerable (cleared DLT). This will apply to patients in the induction (after cycle 1) and maintenance phase only.

### 8.1.4 Dose Adjustment Guidelines for Selinexor-Related Toxicities

**Table 2 Selinexor-related toxicity management guidelines**

Toxicity and Intensity	Dose Modification
Fatigue (common)	
Grade 1	Ensure adequate caloric intake and assess volume status. Rule out other causes of fatigue such as pain, anemia, or adrenal insufficiency.
Grade 2	Ensure adequate caloric and fluid intake and assess volume status. If fatigue does not improve with conservative measures, consider dose reduction selinexor by one level.
Grade 3	Ensure adequate caloric and fluid intake and assess volume status. Interrupt selinexor dosing until resolved to Grade $\leq 2$ , reduce dose of selinexor by 1 level
Anorexia (common)	
Grade 1	Assess dietary options (e.g., try a variety of other foods). Add high-calorie supplements (e.g., Ensure®).
Grade 2	Add high-calorie supplements (e.g., Ensure®). Consider olanzapine 2.5 - 5mg po qhs (especially if nausea or sleep disturbance present). Consider megesterol acetate 400-800mg daily. Consider dronabinol (Marinol®). Skip intermittent doses of selinexor while supportive medications are instituted. If Grade 2 anorexia does not resolve after institution of supportive medications, reduce selinexor dose by 1 level.
Grade $\geq 3$	Interrupt dosing with selinexor. Add high calorie supplements. Use supportive medications alone or in combinations. Restart selinexor at 1 dose level reduction once anorexia resolves to Grade $\leq 2$ . If Grade 2 anorexia persists with supportive medications, reduce dose of selinexor another dose level.
Nausea/Emesis (common)	
Grade 1	5-HT3 antagonists, D2 antagonists, olanzapine 5mg qhs or 2.5mg bid, NK1 antagonists, or dronabinol (Marinol) or combinations can prevent nausea in the majority of patients.
Grade 2	Implement one or more combinations of anti-nausea medications. If nausea does not

	resolve to Grade $\leq 1$ , reduce dose of selinexor by one dose level.
Grade 3	Implement one or more combinations of anti-nausea medications and interrupt dosing of selinexor. Selinexor may be restarted with one dose level reduction when nausea is Grade $\leq 2$ and adequate caloric and fluid intake have been achieved.
Hematologic	
Neutropenia (rare)	
Grade 1 (ANC < LLN - 1500/mm  ) Grade 2 (ANC < 1500 - 1000/mm  ) Grade 3 (ANC < 1000 - 500/mm  )	Maintain dose level The use of growth factors during selinexor treatment is permitted during the phase II and after cycle 1 is completed in the phase I.
Grade 4 (ANC < 500/mm  )	Hold study treatment until ANC returns to >800/mm  . Dose reduce LD (if appropriate) and consider growth factor support.
Febrile neutropenia, or fever of unknown origin without clinically or microbiologically documented infection (ANC < 1.0 x 10  /L, fever $\geq$ 38.5°C)	Hold study treatment until patient has stabilized. Dose reduce LD (if appropriate) and consider a dose reduction in selinexor
Thrombocytopenia (Platelets) (uncommon)	
Grade 1 (PLT < LLN - 75,000/mm  ) Grade 2 (PLT < 75,000 - 50,000/mm  )	Maintain dose level.
Grade 3 (PLT < 50,000 -25,000/mm  ) without bleeding	Maintain dose level
Grade 4 (PLT < 25,000/mm  ) without bleeding	Delay study treatment until resolved to $\leq$ grade 3. Dose reduce LD (if appropriate) and / or selinexor Platelet transfusions may be given to support platelet levels in patients with clear clinical benefit from selinexor.
Grade $\geq 3$ with bleeding	Delay study treatment until resolved to $\leq$ grade 2, reduce dose by 1 level when resolved.
Hyponatremia (common)	
Grade 1 (Lower Limit of Normal to 130nM)	Maintain dose level, assure adequate fluid, electrolyte and caloric intake, adjust other medications, consider salt supplementation, rule out other causes.
Grade 3 (120-130nM)	Discontinue selinexor until resolved to grade $\leq 1$ then consider reducing dose by 1 level

	especially if another cause is not identified. Check renal function, serum and urinary electrolytes, and rule out other causes.
Diarrhea (uncommon)	
Grade 1 (despite maximal anti-diarrheal medication)	At the first sign of abdominal cramping, loose stools, or onset of diarrhea, it is recommended that the patient be treated according to institutional standard of care. Maintain dose level of selinexor.
Grade 2 (despite maximal anti-diarrheal medication)	Hold therapy. If diarrhea returns as $\geq$ Grade 2, then reduce selinexor dose by one dose level until resolved to $\leq$ grade 1
Grade 3/4 (despite maximal anti-diarrheal medication)	Delay selinexor until resolved to $\leq$ grade 2, then follow guidelines above.
Other adverse events	
Grade 1 or 2	Maintain dose level and initiate standard supportive care.
Grade 3	Delay dose until resolved to $\leq$ Grade 1, then reduce by 1 dose level
Grade 4	Discontinue selinexor and rule out other causes. If other causes of Grade 4 adverse event are uncovered, selinexor may be re-initiated at 1 dose level reduction.

All dose modifications should be based on the worst preceding toxicity.
 
Isolated values of <math>\geq</math> grade 3 alkaline phosphatase values will NOT require dose interruption. Determination of liver vs. bone etiology should be made, and evaluation of GGT, 5'NT, or other liver enzymes should be performed.
 
<math>\geq</math> Grade 3 anemia judged to be a hemolytic process secondary to study drug will require interruption of study treatment until resolved to <math>\leq</math>Grade 1. Selinexor may then be re-instituted at 2 levels below original dose.
 
<math>\geq</math> Grade 3 lymphopenia considered clinically significant will require dose interruption until resolved to <math>\leq</math> grade 2, then reduce by 1 dose level.
 
Patients are allowed dose reductions to a minimum dose of 5mg/m^2. If a patient requires a dose interruption of > 28 days, then the patient must be discontinued from the study. Patients who discontinue the study for a study related adverse event or abnormal laboratory value must be followed at least once a week for 28 days and subsequently at 28 day intervals until resolution or stabilization of the event, whichever comes first.
 
a. Common Terminology Criteria for Adverse Events (CTCAE Version 4.03 ) otherwise specified values.
	

- For all  $\geq$  Grade 3 hematological or non-hematological AEs that are NOT selinexor related: After consultation with the principal investigator and at the discretion of the treating physician, selinexor dosing may be maintained provided that the patient can continue to take the agent by mouth, or via other enteral route.

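### In Table 2, the catch-all rows and the notes beneath them give different selinexor instructions for the same events, and nothing says which prevails

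*Combined protocol and SAP*

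**What the plan says.** Section 8.1.4, Table 2 is titled "Selinexor-related toxicity management guidelines". Its hematologic rows deal only with neutropenia (including febrile neutropenia) and thrombocytopenia. Events without their own row come under the heading "Other adverse events". There, Grade 1 or 2 keeps the dose. Grade 3 is delayed until recovery to at most "Grade 1, then reduce by 1 dose level". Grade 4 means discontinuing and looking for other causes, followed by this sentence: "If other causes of Grade 4 adverse event are uncovered, selinexor may be re-initiated at 1 dose level reduction".

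The notes beneath these rows add separate rules:

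- **Drug-induced hemolytic anemia, Grade 3 or higher:** interrupt until Grade 1 or less, after which "Selinexor may then be re-instituted at 2 levels below original dose".
- **Lymphopenia, Grade 3 or higher:** "lymphopenia considered clinically significant will require dose interruption until resolved to" Grade 2 or less, then one level down.
- **Any event of Grade 3 or higher not related to selinexor, hematological or not:** after consultation with the principal investigator and at the treating physician's discretion, "selinexor dosing may be maintained provided that the patient can continue to take the agent by mouth" or another enteral route.

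The corresponding catch-all in Table 3 (Section 8.2.4, liposomal doxorubicin) is headed "Other non-hematologic Adverse Events", and Table 4 (Section 8.3.4, dexamethasone) uses the same heading.

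**The concern.** A dose-modification table should give one instruction per event. Here a site can find a catch-all row and a note that both describe its patient and ask for different things: stop or continue, restart or not, one level down or two, recovery to Grade 1 or to Grade 2.

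At stake is consistent handling of selinexor across the three centres named in Section 3.1. Two patients with the same event could be reduced, stopped or left at full dose depending on which line of the table was read. That affects their safety management, and it makes exposure and discontinuation data harder to interpret.

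**Working it through.** The plan gives no figure to reproduce here. The check sets the rules side by side.

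**Step 1: what the catch-all covers.** Tables 3 and 4 restrict their catch-all to non-hematologic events; Table 2 does not. Table 2 has no row for anemia, leucopenia or lymphopenia, so as written all three fall into the catch-all.

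**Step 2: Grade 4 event with another cause.** The row requires discontinuation and allows a restart one level lower. The bullet allows dosing to continue. Both use permissive wording, so a site that stops and restarts lower breaks neither. A site that continues satisfies the bullet but breaks the row. The table's title limits it to selinexor-related toxicity, but that does not settle the matter, because the row itself legislates for events with another cause.

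**Step 3: the two hematologic forms named in the notes.**

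| Event | Catch-all row | Note |
|---|---|---|
| Drug-induced hemolytic anemia, Grade 3 | wait for Grade 1 or less, 1 level down | wait for Grade 1 or less, 2 levels down |
| Same, Grade 4 | discontinue; no restart, since the drug is the cause | restart 2 levels down |
| Clinically significant lymphopenia, Grade 3 | wait for Grade 1 or less, 1 level down | wait for Grade 2 or less, 1 level down |
| Same, Grade 4, selinexor-related | discontinue | wait for Grade 2 or less, 1 level down |

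Row and note differ in all four lines.

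**Step 4: is precedence stated?** Two sentences come near it. Section 8.1.1 lets the most severe grade decide when different toxicities coincide, and a note under Table 2 bases modifications on the worst preceding toxicity. Both rank toxicities; neither ranks a row against a note.

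**Step 5: suppose each note displaces the row for the form it names.** The double answers in Step 3 disappear. The forms not named remain under the row:

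- **Anemia, Grade 4, drug-related:** non-hemolytic is discontinued; hemolytic may restart 2 levels down. The order is inverted.
- **Anemia, Grade 3:** non-hemolytic goes 1 level down; hemolytic goes 2 levels down. The order is not inverted.
- **Lymphopenia, Grade 3:** the form that is not clinically significant must recover to Grade 1, the significant form only to Grade 2. Inverted.
- **Lymphopenia, Grade 4, selinexor-related:** the non-significant form is discontinued; the significant form restarts 1 level down. Inverted.

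The two lymphopenia inversions disappear if the note is taken to imply that non-significant lymphopenia needs no action. The table does not say so.

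**Step 6: leucopenia.** This compares two rows. Grade 3 leucopenia, under the catch-all, is delayed and reduced. Grade 3 neutropenia, under its own row, keeps its dose. The hematology panel in Section 5 reports white cells and neutrophils together, so one sample can trigger both.

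**The case against.** The strongest reply is that the notes are specific exceptions to general rows. They follow the catch-all rows within the same table, and the alkaline phosphatase note plainly works as an exception. On that reading hemolytic anemia and significant lymphopenia each have one rule, and the qualifier about clinical significance suggests that other lymphopenia was not meant to interrupt dosing. The scheduled hematology panel lists no lymphocyte count, so that case may seldom arise. This is a reasonable reading, but it is not written down, and it leaves the Grade 4 anemia inversion and the leucopenia contrast. Nor does it resolve the Grade 4 conflict in Step 2, where the row and the bullet both address an event with another cause.

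Two stronger readings are tempting, and the documents support neither.

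A reader might infer that anemia, lymphopenia and unrelated events all have two answers, with the milder form always treated more harshly. Non-hemolytic anemia and non-significant lymphopenia have only the row. Grade 3 anemia is ordered normally. Unrelated events have no milder and more serious form to compare.

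A reader might also infer a measurable loss of responders and power. Section 8.1.2 lists anemia and leucopenia at 10% or more with selinexor, and Section 8.2.2 gives anemia as 25% with liposomal doxorubicin. Neither figure carries a grade, and the catch-all changes the dose only from Grade 3. Section 11.3 counts patients with inadequate post-baseline data as failures, not everyone who stops early. Disease is assessed every cycle (Section 6.1.1), and Appendix A asks for two consecutive assessments before new therapy, so a response reached before stopping can still count. Section 9.1.1.2 permits transfusion and erythropoietin, and the closing bullet offers a route to continued dosing for anemia not caused by selinexor.

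**Conclusion.** The point stands as an internal inconsistency in Table 2. The firmest part is the Grade 4 event with another cause, where row and closing bullet disagree and no precedence is given. The differences for drug-induced hemolytic anemia and clinically significant lymphopenia also stand on the text. They rest on two conditions: that the catch-all heading means what it says, and that the notes are not exceptions. If the notes are exceptions, what remains is the Grade 4 anemia inversion, the lymphopenia inversion (subject to the implied-no-action reading) and the leucopenia contrast.

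The practical consequence is that sites could reduce or stop selinexor differently for the same event. Its frequency, and any effect on the overall response rate or on power, cannot be quantified from the documents. The planned sample size and the design's stated error rates are unaffected.

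**What to change.** Reconcile the catch-all rows of Table 2 with the notes beneath them. The amended text should:

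1. state whether the catch-all covers hematologic events, given the narrower heading in Tables 3 and 4;
2. state whether a row or a note prevails when both describe the event;
3. give one answer for Grade 4 events not related to selinexor;
4. make the anemia, lymphopenia and leucopenia instructions explicit, including for forms the notes do not name.

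Which rule applies in each case is for the investigators. The cost is the wording of one heading, one cell and the notes of one table in an amendment. No extra data or patients are needed.
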